When the training is completed, therapists will proceed to schedule post- online supervision for a minimum of 1 case and a maximum of 2 cases over the course of 3 months with one of two clinicians at UCSF. At the 4 week treatment mark for each case, therapists will complete a self-report on FBT fidelity to key components and patient weight change. Therapist video skill assessments related to key components will take place at baseline and at the end of online ET-FBT and end of supervision. Once the therapist completes a minimum of one case, the therapist will receive CE credit and a certificate of completion of FBT training. Therapists who enter the online training protocol will be compensated for their time for the completion of all assessments (\$100 for each assessment point).

UCSF's role in research activities are as such: Two UCSF clinicians will be responsible for conducting individual work with each therapist participant weekly for 1 hour per week for 12 weeks during the supervision timepoint of the study. They will use the published supervision manual for FBT (Forsberg et. al) published by Guilford. They will rate fidelity using a therapist version of self-report (described below) and will rate the recorded responses to the

clinical vignettes (described below). They will have access to all of the fidelity assessments (the self-reports and the vignettes all outline below) in order to complete these ratings. Access will be through RedCap in order to make sure the data they receive is secure and HIPAA compliant in accordance with Stanford's IT recommendations. They will also know the patient weight change data (solely session 1 through 4 weights and dates taken no patient PHI will be collected in the study) as they need this information to teach the therapist using supervision.

Therapists will complete the following measures/assessments:

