Weight change in patients treated pre and post-training: Weight change from sessions 1 to 4 will be collected on one adolescent patient with AN treated pre-training (baseline eligibility) and post online ET-FBT per participating therapist during supervision or within 3 months following completion of supervision. No patient identifying information will be collected. This will take 5 minutes to complete. This measure will be used as the main outcome for treatment (patient outcome) efficacy (Aim 2).

Key component skills: Therapists will be asked to view mock therapy session video clips and play the role of the therapist. These clinical videotapes are actors playing families using a script and usually lasting less than three minutes. The therapist in training watches the video and records their verbal intervention response to the clinical scene. The specific skills assessed are related to how effectively the therapist used externalization or agnosticism (as appropriate clinically) and will be scored by expert clinicians using standardized coding. This was the approach used in our preliminary study. This measure will be completed at BL, ~3 months (end of online training-EOT), and end of supervision (EOS) ~6 months. This is a measure of fidelity and change will be correlated with patient weight change outcome (Aim 3) for target validation.

Key component knowledge: This is a brief 10 question multiple choice measure of knowledge of key components of FBT that was used in our preliminary study. These will be conducted at BL, ~3 months (end of online training-EOT), and end of supervision (EOS) ~6 months. This is a measure of fidelity and change will be correlated with patient weight change outcome (Aim 3) for target validation.

Consultation Questions: The brief 8 questions ask participants about their experience with supervision in the research study. This measure will be administrated at ~3 months (end of training-EOT), and end of supervision (EOS) ~ 6 months.

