In **Aim 1**, we will first examine how well we can retain clinicians in our study. We will consider retaining 50% by end of study (6 months from the baseline) as neither success nor failure and at least 65% as successful retention. We will employ simple one-sample chi-square test (2-tailed, alpha=.05) comparing the sample retention to 50%. We will then examine whether therapist fidelity and competency in implementing FBT significantly improves from pre training to post training. For this investigation, we will employ longitudinal mixed effects modeling, which enables us to fully utilize outcome data repeatedly measured for most clinicians (3 assessments: 0 (pre), 3 and 6 month). Data points that are missing due to clinician attrition or intermittent dropout will be handled assuming that data are missing at random conditional on observed information. In this procedure, all available cases including the ones with missing information will be included in the analyses. We believe such missing data assumption is reasonable given that we will include variables (e.g., clinician fidelity/competency) supposedly related to attrition in our mixed effects modeling. Nonetheless, as a way of sensitivity analysis, we will conduct mixed effects analyses with and without including other possible predictors of attrition, which we believe is important to support the validity of our study findings as we expect a considerable level of attrition. For estimation of mixed effect models, we will employ maximum likelihood (ML) estimation embedded in the Mplus program.

In **Aim 2**, using the same mixed effects modeling approach, we will examine whether the patient outcome (weight gain) significantly improves from pre to post training.

In **Aim 3**, we will examine the relationship between the changes in clinician outcomes (fidelity/competency) and the change in patient outcome (weight gain). This will be investigated in the latent variable modeling framework, by formally relating the parallel longitudinal processes (esp. by correlating the slopes) of patient and clinician outcomes. This investigation is of particular

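### No rule says which post-training patient supplies the Aim 2 weight outcome, so the case can be chosen after randomization and an early-ended case passed over without counting as missing

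*Protocol*

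**What the plan says.** **Outcome.** The weight-change item under Treatment Outcome Measures in the Protocol states: "Weight change from sessions 1 to 4 will be collected on one adolescent patient with AN treated pre-training". It asks for one post-training case as well, "per participating therapist during supervision or within 3 months following completion of supervision". This is the main patient outcome for Aim 2.

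**Number of cases and reporting.** The Protocol's supervision paragraph schedules supervision "for a minimum of 1 case and a maximum of 2 cases over the course of 3 months". It adds: "At the 4 week treatment mark for each case, therapists will complete a self-report on FBT fidelity to key components and patient weight change". It then says: "Once the therapist completes a minimum of one case, the therapist will receive CE credit and a certificate of completion of FBT training". What completing a case means is not defined.

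**Patient data.** The paragraph on the collaborating site's role describes the weight data as "solely session 1 through 4 weights and dates taken no patient PHI will be collected in the study".

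**Index patient.** The Working Alliance Inventory item identifies the patient it refers to only as the one whose post-training weight change was supplied.

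**Pre-training case.** The eligibility paragraph requires weight gain over weeks 1 to 4 from a patient the therapist has already treated, or treats before training starts.

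**Analysis.** The SAP lists a comparison between randomized groups in Aim 2. The Data Analytic Plan uses the Aim 1 mixed model for weight gain. Its missing-at-random statement concerns "Data points that are missing due to clinician attrition or intermittent dropout". It gives no rule for choosing between two cases and does not mention patients who end treatment early.

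**The concern.** One outcome slot can be filled from more than one patient, and the plan does not fix which. The arm is disclosed to the therapist before training begins, and the therapist reports the weights. Selection of the outcome case therefore happens after randomization and unblinded, so randomization does not protect the arm comparison against it.

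If the first patient is admitted or the family stops before session 4, a second supervised patient, or one seen in the three months after supervision, can supply the value. The therapist then has a complete record and the mixed model has nothing to handle. Credit and certification also depend on completing a case, which is some reason to prefer one that runs its course.

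The Aim 2 arm comparison and the pre-post change are both exposed, as is Aim 3, which relates fidelity change to the same weight outcome. There is also a loss of information. The share of started cases reaching session 4, by arm, is something a later trial would need, and the retention criterion in Aim 1 counts only clinicians.

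**Working it through.** The documents state no sample size, SD, effect size or patient loss rate for Aim 2, so there is no figure to reproduce. The check has two parts.

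**1. What the passages fix and leave open**

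| Question | Text | Settled? |
|---|---|---|
| How many post-training patients enter Aim 2? | Outcome item: one. Supervision paragraph: one or two, each reported | Not reconciled |
| Which one, if there are two? | Nothing in either document | No |
| Latest permitted case | Three months after supervision ends | Yes |
| Time basis of the outcome | Outcome item: sessions 1 to 4. Eligibility: weeks 1 to 4. Supervision paragraph: 4-week mark | Not reconciled |
| Disposition of a case that ends early | Weights and dates only | Not captured |
| Patient-level missing weight | SAP names clinician attrition or intermittent dropout | Not addressed |

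If the first case ends early and no other is supplied, the therapist's post-training value is missing and the mixed model handles it under missing at random. If another case is supplied, no value is missing and the model cannot detect the switch.

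**2. How large the effect could be (illustration; all rates assumed)**

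Suppose weight change is normal, and the lowest fraction d of cases is lost and replaced by cases that reach session 4. The mean of those recorded then rises by

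shift(d) = φ(z_d) / (1 − d), in SD units,

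where z_d is the d-quantile of the standard normal and φ its density.

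- d = 5%: 0.1031 / 0.95 = 0.109 SD
- d = 10%: 0.1755 / 0.90 = 0.195 SD
- d = 15%: 0.2332 / 0.85 = 0.274 SD
- d = 20%: 0.2800 / 0.80 = 0.350 SD

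If the tendency to be lost correlates only ρ with weight change, multiply by ρ.

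*Between arms*, 15% against 5%: 0.2743 − 0.1086 = 0.166, about 0.17 SD. With ρ = 0.5 this is 0.083 SD, and with ρ = 0.3 it is 0.050 SD. For an assumed SD of 1.5 kg the first figure is 1.5 × 0.166 = 0.25 kg. With equal loss in both arms it is zero.

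*Pre to post*, post shift minus pre shift:

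- 10% pre, 10% post: 0
- 10% pre, 20% post: 0.350 − 0.195 = +0.155 SD
- 5% pre, 20% post: 0.350 − 0.109 = +0.241 SD
- 20% pre, 10% post: 0.195 − 0.350 = −0.155 SD

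*Better of two cases reported*: 1/√π = 0.56 SD if the two are independent. This is an extreme case, since it requires every therapist to have two cases and supply the better one; correlation within therapist would lower it.

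**The case against.** The strongest reply is that the plan nowhere provides for replacement. A maximum of two cases may simply mean two supervised cases, and a weight report is requested at four weeks for each. That is correct: substitution is permitted by silence, not prescribed.

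Two stronger readings are therefore tempting but unsupported.

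- A reader might infer that a failed case is recorded nowhere. The request for a report on each case, the dated session weights, and weekly supervision all suggest that a supervised case ending early could leave some data. Because parts of the Protocol count weeks and not sessions, such a patient might even have a 4-week weight.
- A reader might infer that the worst outcomes vanish from safety reporting. The serious adverse event wording is not limited to participants, deaths and suicide attempts go at once to the DSMB and IRB, and none of this depends on reaching session 4.

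It is also fair to say that both arms are offered the same supervision, that no document gives a reason for loss to differ threefold between arms, and that the pre-training case is itself selected on having data. A one-directional bias is therefore not established. Finally, this is a feasibility study, and its Aim 2 comparison has no stated size or power.

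What remains is the missing rule. Two reports and one slot, with no statement of which report counts, is a gap on any reading. The pre-training case does not repair the arm comparison: as an eligibility item it belongs before randomization, whereas the post-training choice comes after it.

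**Conclusion.** The point holds as a gap in case definition and disposition recording. The Aim 2 patient is not fixed in advance, can be chosen after randomization by an unblinded therapist, and can displace a patient who was admitted or stopped early without any value appearing as missing. Why a case ended is not among the specified patient data.

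The arm comparison is biased only if case choice or early loss differs by arm. The pre-post change is biased only if selection differs between the two periods. Neither size nor sign follows from the documents. The figure of about 0.17 SD rests on assumed losses of 5% and 15%, a normal outcome, and loss of exactly the lowest gainers; it shrinks in proportion to a weaker link between loss and gain. The change is worth making because it is cheap and because an unregistered case may not be recoverable once data collection is over.

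**What to change.** **Protocol, weight-change item.** Define the Aim 2 case as the first eligible adolescent the therapist starts after training, registered without identifiers at session 1 and not replaceable by a later case. Reconcile this item with the supervision paragraph on one patient against each case, and on sessions 1 to 4 against the 4-week mark, and align the week-based wording of the eligibility paragraph.

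**Data collection.** For every started case, record whether session 4 was reached and, if not, the reason (admission, family stopped, transfer, other) and the last weight with its date. Ask the same of the pre-training case.

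**SAP.**

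- Report by arm the number of started cases, the proportion reaching session 4, and the reasons for not doing so.
- In Aim 2, treat the session 4 outcome of an index case that ended early as missing in the mixed model, using its recorded weights where available.
- Add a patient-level missing-not-at-random sensitivity analysis that shifts the unobserved outcomes over a stated range, separately by arm.
- Do not make the last available weight the primary value: it compares unequal durations, and a case ending after session 1 would score zero change.

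**Cost.** Two short REDCap items and some SAP wording. Some index-case outcomes will be missing that a later patient would have filled, and the mean gain may look less favourable.

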# Implementing Family-Based Treatment for Adolescent Anorexia Nervosa for Providers in Private Practice: A Feasibility Study

Study Protocol

NCT04428580

June 9, 2020

We will employ the same recruitment strategy that was successful in our initial study and advertise throughout the United States (US) on the Academy for Eating Disorders (AED) websites, Eating Disorder Research Society (EDRS) listserve, and the National Eating Disorder Association (NEDA) listserve. In addition, we will use Facebook and Twitter advertisements to augment these approaches.

Therapists will be trained in one of two ways for this study: 1) online training x 3 months, followed by expert supervision for 3 months; or 2) recorded webinar training provided in 12 1-hour webinar lectures provided weekly, followed by expert supervision for 3 months. UCSF, listed as a collaborating institute, will aid in training and supervising the participating therapists in one of these two arms of Family-based Treatment training (see description of research activities at UCSF below).

Therapists are eligible to participate if they have completed a masters or doctoral training in their field (psychology, psychiatry, family therapy, social work), are licensed in their respective state, have no reports of malpractice or loss of privileges at relevant clinical institutions, have computer/web access for online training and assessments and no previous 2-day in-person workshop training in FBT, and submit baseline data on weight gain from week 1-4 from a previously treated adolescent with AN they have treated in the last 6 months or alternatively one that they treat within 3 months of the initial screening before starting the training. Therapists who have had previous training in FBT are not eligible to be randomized.

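### Therapists who stop before a supervised case reaches week 4 have no described route to the post-training weight, so Aim 2 inference for all randomised therapists rests on an untested missing-at-random assumption

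*Protocol*

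**What the plan says.** **Pre-training weight.** To be eligible, a therapist must "submit baseline data on weight gain from week 1-4 from a previously treated adolescent with AN they have treated in the last 6 months". A case treated within 3 months of screening, before training starts, also qualifies. Every randomised therapist should therefore have a baseline value, taken from a different adolescent than the post-training one.

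**Post-training weight.** Under Treatment Outcome Measures, the Protocol takes it on one patient "per participating therapist during supervision or within 3 months following completion of supervision", and names weight change as the main patient outcome for Aim 2.

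**Entry to supervision.** The Protocol's supervision paragraph says: "When the training is completed, therapists will proceed to schedule post- online supervision for a minimum of 1 case and a maximum of 2 cases". Supervision runs "weekly for 1 hour per week for 12 weeks during the supervision timepoint of the study".

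**When weight is reported.** The same paragraph says: "At the 4 week treatment mark for each case, therapists will complete a self-report on FBT fidelity to key components and patient weight change".

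**Analysis.** The SAP's Aims section compares weight gain before and after training and between the randomised groups. The Data Analytic Plan applies to Aim 2 the mixed-model approach set out for Aim 1. That approach uses maximum likelihood (ML) and retains all available cases, and "Data points that are missing due to clinician attrition or intermittent dropout will be handled assuming that data are missing at random". The conditioning is on what has been observed. The sensitivity analysis refits the models with and without further predictors of attrition. The SAP anticipates substantial attrition, treats 50% retention at 6 months as neutral and calls 65% or more a success.

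**The concern.** The collection window for the main patient outcome is defined by progress through the intervention, not by time since randomisation. A therapist who does not reach supervision cannot report a weight during it, and the three-month extension never opens because supervision was not completed. The same applies to one who leaves supervision before any case reaches its fourth week. Such a therapist may still treat an adolescent with anorexia nervosa, but the Protocol does not ask for that weight.

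The gap matters in this trial for three reasons. Attrition is expected to be substantial. One format is self-paced and the other is released weekly, so the arms could plausibly lose different numbers or kinds of therapist. Aim 2 also compares the randomised arms. All observed post-training weights will come from therapists who got as far as supervision, and what the model says about the others is extrapolation under MAR.

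**Working it through.** The documents state no sample size, weight effect or SD for Aim 2, so there is no planned figure to reproduce. The check has three parts.

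**1. Route to the outcome, by stage of stopping**

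| Where the therapist stops | Weight during supervision? | Weight in the 3 months after completed supervision? |
|---|---|---|
| Before finishing training | No, supervision not started | No |
| After training, never starts supervision | No | No |
| In supervision, before any case reaches week 4 | No | No |
| In supervision, after a case reaches week 4 | Yes, already reported | Not needed |
| Completes supervision | Yes | Yes |

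The first three rows have no described route.

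**2. What the planned model can and cannot repair**

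This is a simulation of 1,000,000 therapists with one pre and one post value. The assumptions are a true change of 0.30 SD, a pre-post correlation of 0.2 or 0.5, and 65% or 50% with a post value. These two fractions borrow the SAP's retention benchmarks, on the assumption that loss to retention means no post-training weight. The ML estimate regresses post on baseline among those observed and evaluates it at the mean baseline of all randomised.

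| Loss depends on | Observed | ML (corr. 0.2 / 0.5) | Completers only (corr. 0.2 / 0.5) |
|---|---|---|---|
| Chance | 65% | 0.30 / 0.30 | 0.30 / 0.30 |
| Chance | 50% | 0.30 / 0.30 | 0.30 / 0.30 |
| Baseline weight gain | 65% | 0.30 / 0.30 | −0.02 / 0.10 |
| Baseline weight gain | 50% | 0.30 / 0.30 | −0.15 / 0.02 |
| Unseen post-training value | 65% | 0.69 / 0.62 | 0.62 / 0.50 |
| Unseen post-training value | 50% | 0.85 / 0.76 | 0.75 / 0.58 |

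ML removes bias that runs through observed data. It does not remove bias from dropout that depends on the unseen weight.

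The last two rows assume strong selection. At correlation 0.2 and 65% observed, the completer bias is 0.622 − 0.300 = 0.322 = (1 − 0.2) × m, so m = 0.40 SD. The gap between observed and missing therapists is then 0.40 / 0.35 = 1.15 SD. These rows show the direction of the problem and are not a forecast of its size.

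**3. Between-arm illustration with a milder gap**

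Let a fraction p of an arm stop, and let stoppers average d below that arm's completers.

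- Mean over all randomised = completer mean − p·d.
- If baseline data do not explain the dropout, the estimate for the arm is close to the completer mean, so its bias is p·d.
- Spurious arm difference = d × (p₂ − p₁).

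Assumed values are p₁ = 0.20, p₂ = 0.40 and d = 0.3 to 0.5 SD.

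- d = 0.3: 0.3 × (0.40 − 0.20) = 0.06 SD
- d = 0.5: 0.5 × (0.40 − 0.20) = 0.10 SD

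**The case against.** Several stronger readings are tempting, and the documents do not support them.

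- **Aim 2 is a completer analysis.** A reader might infer this because post-training weights come only from those who reach supervision. The SAP retains all available cases, and therapists who stop contribute their baseline weight. The second part of the working shows that ML and a completer analysis can give very different answers. The SAP also expects to include variables such as clinician fidelity or competency, so the model need not rely on the baseline weight alone.
- **Anyone who leaves supervision midway has no outcome.** Weight is reported at each case's fourth week within a 12-week supervision, so later leavers can already have contributed.
- **Stopping training also stops the clinician assessments.** These carry approximate 3- and 6-month labels as well as end-of-training and end-of-supervision ones, and no text ends them when training stops. The Protocol's adverse-event paragraphs treat discontinuing a training and leaving the study as separate decisions. That weakens this reading. It also shows that a therapist can be off training yet in the study, with no weight schedule.
- **A larger arm bias.** Using d × [p₂/(1 − p₂) − p₁/(1 − p₁)] gives d × (0.667 − 0.250) = 0.12 to 0.21 SD. That formula needs d to be the shortfall from the mean of all randomised in the arm. Measured against completers, as here, it does not apply.
- **A quantified overstatement of the training effect.** If non-finishers do not change at all, a finisher-only estimate overstates the all-randomised change by 1/0.65 = 1.54 to 1/0.50 = 2.00. This takes retention benchmarks as rates of missing weights, assumes no change in non-finishers, and describes an estimator that the SAP does not use.

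The best remaining objection concerns the estimand. Aim 2 is about weight gain in sessions of FBT, and someone who left after one lecture may have no FBT case. This has limited force, because the pre-training case also comes from a therapist not yet trained in FBT. It does mean that the requested case must be defined. It is also true that some therapists who stop will not return a form or will have no eligible patient. That limits the gain from the fix but does not remove the gap.

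**Conclusion.** The point holds in a limited form. For therapists who stop training, never start supervision, or leave before a case reaches week 4, the Protocol describes no way to obtain the main patient outcome. They remain in the model through baseline data and any covariates, so conclusions about all randomised therapists, including the arm comparison, rest on MAR. The one planned sensitivity analysis changes the set of attrition predictors but never departs from that assumption.

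The size cannot be derived from the documents. Under the assumed 20% and 40% stopping rates, a 0.3 to 0.5 SD deficit against completers, and dropout not explained by baseline data, the spurious arm difference is about 0.06 to 0.10 SD. It is zero if stopping rates and deficits are equal in the two arms, although the pre-post change in each arm would still be biased by p·d. This is an inexpensive improvement worth making in a feasibility study. It does not invalidate the design.

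**What to change.** 1. Amend the Protocol's supervision paragraph and its weight-change entry. Every randomised therapist would be asked for the session 1 to 4 weights of one adolescent with anorexia nervosa treated after the training period, up to about month 9 from randomisation (3 months of training + 3 of supervision + the existing 3-month extension). The request would apply whatever their training or supervision status, and only withdrawal of consent to data collection would end it.
2. State that the assessments at about 3 and 6 months are sought on the same basis.
3. In the SAP, report missing post-training weights by arm and by stage of stopping, and carry a flag for completion of training and supervision.
4. Add one sensitivity analysis that departs from MAR. For example, shift the values implied for therapists without a post-training weight downward by a range such as 0 to 0.5 SD, separately by arm, and report where the Aim 2 conclusions change.

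The cost is protocol wording, reminders, a five-minute form and possibly some further payments at the existing $100 per assessment point. The downside is that some of the added cases will have been treated without supervision, which is why the completion flag is needed. Some therapists who stop will have no eligible patient, so missing data will be reduced but not eliminated.
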